Procedural steps	
Procedural steps for the Corrie Digital Health group:
 
 a. Patients presenting with acute myocardial infarction as the primary diagnosis for admission to a participating site, and meeting other eligibility criteria, will be recruited b. Participants must be approved to participate in this research study by his/her primary care team 
 - As resources allow, to make participation possible for participants who are not iPhone owners, we will offer an "iShare" device share program wherein we loan an iPhone along with the Apple Watch during the study period - We will also introduce a family and friends program wherein we offer the app (but not Apple Watch) to family and friends who have an iPhone and would like to use the app for the purpose of supporting the participant (participant must agree and designate the family/friend, including email and phone number, in the app) c. If the participant passes screening questions for study inclusion (i.e., owns a

smartphone and not limited from normal smartphone usage due to conditions such as visual, motor, auditory impairment), the participant will proceed to e-Consent

d. e-Consent will be done through ResearchKit on a study iPad

e. The study team member will be present to guide the participant and give the participant an opportunity to ask questions before having the participant sign the consent form. If consent is provided, a Corrie sign will be placed on the door or in the room to indicate study participation to clinical staff or an Epic research flag will be placed.

f. Next, the study team member will guide the participant through download of the app, and setup of the app including inputting medications and profile information. Participants will also be given a StartKit (See Supplemental Study Documents) which will include information on how to use the app to reference following discharge.

g. Consenting participants will be given an Apple Watch, Silicone Healthband, and iHealth blood pressure monitor (FDA approved), and will be instructed to wear the Apple Watch/Silicone Healthband on their non-dominant wrist. The Apple Watch and iHealth blood pressure monitor will be paired with the iPhone.

h. To promote privacy of health information a login will be required for access to app (created upon e-consent) and the iPhone will be set to password protected mode / touch ID activated

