- v. After study completion, participants will participate in a phone interview, if they agree, to gather more information about their experience, using a standardized set of questions (see Supplemental Study Documents).
- w. Participants may be given the option to participate in future research studies.

Data collection for the Corrie Digital Health group and the historical standard of care comparison group to assess the primary outcome:

- a. Following study completion, we will submit requests to Johns Hopkins Hospital and Johns Hopkins Bayview Medical Center, Massachusetts General Hospital Partners group, and Reading Hospital administrative data managers to obtain the following data on both groups: age, sex, race, language, body mass index, marital status, smoking status, diagnosis of STEMI versus NSTEMI, insurance status (payor index), admission date, discharge date, type of intervention received in hospital (PCI or CABG), a discrete count of AHRQ identified Elixhauser comorbidities based on ICD-9-CM and ICD-10 diagnosis codes, discharge disposition, readmission, days to readmission, reason for readmission, ED visits, observation visits, and mortality.
- b. These variables will be obtained for both groups via the administrative databases to ensure standardization of variables and collection.
- c. For the historical control group we will query data for patients admitted to each hospital from October 1, 2015 to October 1, 2016 for a STEMI or NSTEMI. To obtain data for the Corrie Digital Health group, 30 days after the last enrolled participant is discharged from the hospital, we will send a list of

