	
participant identifiers to the hospital data managers.
 
d. In an ancillary study restricted to both groups of Hopkins participants, we will perform an Epic data extraction focused on measures of 2018 AHA/ACC guideline-directed cholesterol management such as serum lipid values upon admission through 12 months of hospital discharge, whether patients were on lipid lowering therapy at the time of admission, prescription of lipid lowering therapies at the time of discharge including statins and non-statins, whether the statin was a high intensity statin regimen at the time of hospital discharge, if patients were not on statin therapy due to a history of side effects, very high risk vs not very high risk status, and whether additional lipid lowering therapies were prescribed within 12 months of hospital discharge.
 
Data collection for patients who were deemed ineligible/declined to participate in the Corrie Digital Health group to assess selection bias:
 
a. Following study completion, we will submit requests to Johns Hopkins Hospital and Johns Hopkins Bayview Medical Center administrative data managers to obtain the following data on the 541 patient who were deemed ineligible/declined to participate in the Corrie intervention group: age, sex, race, marital status, smoking status, diagnosis of STEMI versus NSTEMI, insurance status (payor index), readmission, days to readmission, and reason for readmission.
 
b. These variables will be obtained via the administrative databases to ensure standardization of variables and collection to those who were enrolled in the Corrie intervention group.

--	--

MiCORE Reading Hospital cohort:

Reading Hospital is participating in this study through a grant from the Reading Hospital Foundation. The participation of patients recruited from Reading will be limited to the 30-day (approximate) initial enrollment period. The data collected from this cohort will be used to support the study’s primary outcome: 30-day readmission rate.

Study procedures for Reading Hospital	
Study design	Same as for primary cohort

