Study duration	Each participant will join the study for the entirety of their hospitalization following enrollment. This inpatient phase will last approximately 1 to 5 days, depending on the length of stay and the enrollment date, with the goal being to enroll the patient participant as early as possible in his/her hospitalization. Then enrollment will continue for 30 days following discharge for an approximate study duration of 30 to 40 days.
Routine care	Same as for primary cohort
Treatment failure or participant removal criteria	None (same as for primary cohort)
Participants receiving therapy when study ends or if a participant’s participation in the study ends prematurely	Same as for primary cohort
Procedural steps	Same as for the Corrie Digital Health group in the primary cohort, paragraphs a through n, and r through w. The Reading cohort will not participate in the procedural steps for the 6 and 12-month follow-ups, as described in paragraphs p and q.

	Data collection for the Corrie Digital Health group and the historical standard of care comparison group to assess the primary outcome will be the same.
--	--

5. Inclusion/Exclusion Criteria

a) The Corrie Digital Health group

Inclusion Criteria	Exclusion Criteria
-Patient admitted for acute myocardial infarction; MI present at the time of admission and Type I NSTEMI or STEMI -18 years or older - smartphone ownership	-Non-English speaking -Visual, hearing, or motor impairment which precludes use of the intervention -Persons not able to participate on due to severity of illness (e.g., intubated and on sedation in the setting of cardiogenic shock)

b) The Historical Comparison group

Inclusion Criteria	Exclusion Criteria
-Patient admitted for acute myocardial infarction; MI present at the time of admission and NSTEMI or STEMI -18 years or older	-Non-English speaking

6. Drugs/ Substances/ Devices

- a. The rationale for choosing the drug and dose or for choosing the device to be used.
- b. Justification and safety information if FDA approved drugs will be administered for non-FDA approved indications or if doses or routes of administration or participant populations are changed.
- c. Justification and safety information if non-FDA approved drugs without an IND will be administered.

Devices: Smartphone + Apple Watch + Silicone HealthBand + iHealth BP monitor +/- Apple TV

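### The Corrie and historical groups enter under different eligibility rules, and the planned matching is not specified or supplied with data well enough to rule out residual selection bias in the primary hazard ratio

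*Combined protocol and SAP*

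**What the plan says.** **Eligibility.** Section 5(a) limits the Corrie group to "MI present at the time of admission and Type I NSTEMI or STEMI" and to smartphone owners. It excludes visual, hearing or motor impairment that prevents use of the intervention, and "Persons not able to participate on due to severity of illness". Section 4, procedural step b, adds that "Participants must be approved to participate in this research study by his/her primary care team", and e-consent follows. A device-share scheme softens the phone rule, but only in part: "As resources allow, to make participation possible for participants who are not iPhone owners". Section 5(b) asks of the historical group only "MI present at the time of admission and NSTEMI or STEMI", age 18 or over and English. Section 4, data collection item c, obtains that group by query: "we will query data for patients admitted to each hospital from October 1, 2015 to October 1, 2016 for a STEMI or NSTEMI". Both lists share English language, adult age, and admission for an acute MI already present at admission.

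**Data and analysis.** The Section 4 request for both groups covers age, sex, race, language, BMI, marital status, smoking, STEMI/NSTEMI, payor, PCI/CABG and "a discrete count of AHRQ identified Elixhauser comorbidities based on ICD-9-CM and ICD-10 diagnosis codes, discharge disposition", among others. Section 7 says that concurrent and historical controls will be matched for the readmission comparison on sociodemographic and clinical variables and on an APR DRG/severity-of-illness score. It then plans a Cox comparison of Corrie against historical patients.

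**Patients not enrolled.** To assess selection bias at the two Hopkins hospitals, Section 4 requests demographics, MI type, payor and readmission for the "541 patient who were deemed ineligible/declined to participate in the Corrie intervention group".

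**The concern.** App users against the historical group is the primary objective (Section 2), and Section 7 sizes that contrast at the two-sided 5% level. If patients who could not have joined the Corrie group are readmitted more often, a hazard ratio below 1 partly reflects who was allowed into each group.

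Matching is the planned remedy, and as written it has three gaps:
- The one named risk score is not among the requested fields.
- The full list of matching variables is not given.
- The Cox sentence mentions neither the matched set nor covariates.

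Type I status, impairment and smartphone ownership are not requested for the historical group either, so matching cannot act on them directly. The data on the 541 patients bear on selection, but no use of them for the primary estimate is stated.

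**Working it through.** **1. The plan's own figure.** Inputs from Section 7: 200 v 1,000 patients, 10% drop-out, 85% of comparison patients event-free, hazard ratio (HR) 0.5, two-sided 5%.
- After drop-out: 180 v 900. Corrie event-free proportion at HR 0.5 = 0.85^0.5 = 0.922.
- Events d = 180 × 0.078 + 900 × 0.15 = 14.0 + 135 = 149.
- Schoenfeld: power = Φ(|ln 0.5| × √(149 × 5/36) − 1.96) = Φ(3.15 − 1.96) = 88%. Without drop-out it is 91%.

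The stated figure of around 90% reproduces by this formula. The point here concerns validity, not the sample-size sum.

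**2. The two groups side by side.**

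| Rule | Corrie | Historical | In the Section 4 request for both groups? |
|---|---|---|---|
| Type I MI | required | not required | no (STEMI/NSTEMI only) |
| Smartphone | required, loans as resources allow | not required | no |
| Precluding impairment | excluded | not excluded | no |
| Too ill to take part | excluded | not excluded | indirectly (comorbidity count, procedure) |
| Care-team approval, consent | required | did not exist | no |
| APR DRG/severity score | to be matched on | to be matched on | no |

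**3. Illustration of size.** The documents give no inputs for this, so the following are assumptions: a share f of historical patients would fail the Corrie rules, their hazard is k times that of the rest, the app has no effect, and historical 30-day risk is 15%. Solve (1−f)e^(−h) + f·e^(−kh) = 0.85 for h, the cumulative 30-day hazard of patients who meet the rules. The apparent HR is h/(−ln 0.85) = h/0.1625. The chance of a false benefit is Φ(−1.96 − ln(HR) × √(d × 5/36)), with d = 180(1−e^(−h)) + 135.

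- *Matching removes half the excess log-hazard* (f = 0.3, k = √2 = 1.41): h = 0.1449, HR = 0.89, d = 159, chance Φ(−1.96 + 0.54) = 7.8%. A simulated log-rank test (20,000 runs, exponential times, censored at 30 days) gives 6.4%.
- *No matching, as a limit for the same scenario* (f = 0.3, k = 2): h = 0.1263, HR = 0.78, d = 156, chance Φ(−1.96 + 1.18) = 21.6%; simulated 17.2%.
- *No difference in hazard* (k = 1): HR 1.00, no bias.
- *Opposite direction* (f = 0.3, k = 0.8): HR 1.06, against the app.

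Other unmatched inputs run from HR 0.91 (f = 0.2, k = 1.5) to 0.64 (f = 0.4, k = 2.5).

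**4. Sensitivity of the half-removed case.** Fix the eligible hazard at 0.1263 instead of the overall risk at 15%. Control event-free proportion = 0.7e^(−0.1263) + 0.3e^(−0.1786) = 0.868, so HR = 0.1263/0.1417 = 0.89. With 180 v 900, d = 180 × 0.119 + 900 × 0.132 = 140 and the chance is Φ(−1.96 + 0.51) = about 7%. The result does not depend on that modelling choice.

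**The case against.** The strongest reply is that the investigators have already seen the problem. They plan matching, draw common covariates for both groups from administrative data, and collect readmission on patients not enrolled for the express purpose of assessing selection. Some residual confounding survives in any historical comparison, and this one is labelled observational and primarily descriptive. That stands in part: the point is not that selection was overlooked. What remains is that the plan as written does not connect these safeguards to the primary hazard ratio, and it names a matching score that it does not request.

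The illness exclusion may also matter less than it looks. Its example is an intubated, sedated patient in cardiogenic shock; time at risk starts at discharge, so in-hospital deaths never count; and nothing bars enrolment after recovery. This is fair, and it is one reason the size is unknown.

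Three stronger readings are tempting and not supported:
- A reader might take HR 0.78 and a 17-22% false-benefit chance as the expected distortion. Those figures assume no matching, which is not the planned analysis.
- A reader might infer that the severity score will be unavailable. Its absence from the request is an inconsistency between Sections 4 and 7, not proof of that.
- A reader might set 541 against the target of 200 and conclude that most historical patients would have failed the Corrie rules. The 541 come from two hospitals and combine ineligible with declined patients, and the documents do not say that the 200 came from the same screening pool.

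**Conclusion.** The concern holds as a risk of residual selection bias in the primary hazard ratio that the plan could cheaply reduce. The differing eligibility rules, the missing severity field and the silence of the Cox sentence on matching or adjustment can all be read directly from Sections 4, 5 and 7. The size is not known. Under the assumed 30% share, twice the hazard and half the excess log-hazard removed, a null app would show an HR of about 0.89 with a 6-8% chance of a false benefit; the share, the hazard and the half are all assumptions.

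A reader might infer that the result must favour the app. That direction is plausible, but the documents do not establish it, and equal or lower hazard among those who fail the rules would give no bias or bias the other way. It should be fixed before the data are requested; confidence is medium because only the size and direction are uncertain.

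**What to change.** 1. Apply to the historical group, and identically to the Corrie group, each Corrie criterion that can be recovered from recorded data, where it is recorded (for example Type I status and coded impairment).
2. Add the APR DRG/severity score to the Section 4 request for both groups, so that the Section 7 matching can be done.
3. State that the primary Cox model is run on the matched set and/or adjusted for the baseline variables already requested: age, sex, race, BMI, marital status, smoking, STEMI/NSTEMI, payor, PCI/CABG and Elixhauser count.
4. In the pull on the 541 patients, flag ineligible and declined separately and add the Elixhauser count and PCI/CABG, as a supportive check on the size of selection.
5. State as limitations that smartphone ownership, care-team approval and consent remain uncorrected.

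**Cost.** Protocol wording and a few fields in pulls already planned. The real price is power at HR 0.5. In the 30%, twice-the-hazard case the remaining historical risk is 11.9%. By Schoenfeld:
- 180 v 630: d = 11.0 + 74.7 = 86, power 76%, down from 88%.
- 180 v 900, if the query pool is large enough to leave 900 eligible controls: d = 11.0 + 106.8 = 118, power about 80%.
- 1:3 matching (180 v 540): d = 75, about 74%. 1:1 (180 v 180): d = 32, about 50%.

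A simulated log-rank test is lower throughout but shows a similar loss (76% before restriction, 62% at 180 v 630). Covariate adjustment or a high control ratio is therefore preferable to 1:1 matching. Type I status and coded impairment may be incompletely recorded for 2015-16, which limits what item 1 can achieve.

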Primary objective: To assess time to first readmission within 30 days post-discharge from the hospital in patients recovering from acute myocardial infarction who use the mobile application as compared to a historical standard of care comparison group.

Secondary objectives: To assess medication adherence, patient satisfaction scores, app usability, patient activation, user engagement, user knowledge, and cost-effectiveness in patients recovering from acute myocardial infarction who use the mobile application. To assess recurrent myocardial infarction, ED visits, observation visits, and mortality in both groups.

3. **Background** (briefly describe pre-clinical and clinical data, current experience with procedures, drug or device, and any other relevant information to justify the research)

Nearly 20 percent of the 39 million patients discharged from the hospital in the US yearly are subsequently readmitted within 30 days with cardiac patients among the leading subset of patients with early readmissions. Current evidence raises major patient safety concerns with the discharge process and rate of avoidable morbidity and mortality. Furthermore, the cost to healthcare system is \$17.4 billion annually and accounted for 17 percent of total hospital payments from Medicare. Improving hospital discharge will likely reduce the rate of early hospital readmission which has been identified as a high priority for the US healthcare system to improve patient safety and reduce avoidable healthcare expenditures.

[name], MD, MHS, PI, has an extensive clinical research experience and experience in clinically testing mobile health technology, including a blinded, randomized mHealth Activity Trial (mActive), and evaluation of the Instant Blood Pressure mobile application. [name] leads the Cardiology mHealth Interest Group at Johns Hopkins which brings together multiple disciplines from

through the University. [name] also completed a HEXCITE Fellowship with Johns Hopkins Medicine and Technology Innovation Center focused on developing skills in designing, testing, and implementing mobile health projects with patients.

4. Study Procedures

Study design	A 1-month observational study, with a historical comparison group, involving Johns Hopkins Hospital and Johns Hopkins Bayview, as well as Massachusetts General Hospital, Reading Hospital, Franklin Square Hospital, and Union Memorial Hospital

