-Corrie is available for iPhone and will be available for Android. -The Apple Watch is only available for iPhone users. -The Silicone HealthBand is an optional component of the program available to all participants. -The iHealth BP monitor is available to all participants through a layered app. -As the Corrie app includes Hopkins-approved Emmi educational videos for AMI patients, and there may be an enhanced experience by participants (possibly along with friends and family) watching these videos on the television monitor in their hospital room, we will pilot installation of Apple TVs to allow the participant to AirPlay the video to the television monitor. -In discussion with an FDA-consultant, because the functionality of the application is as an organizational and navigational tool for patients, it does not require pre-approval from FDA before use with patients. It falls within the category of mobile applications for which the FDA is exercising enforcement discretion. - Patients meeting the eligibility criteria with an iPhone will receive the App, and the Apple Watch/Silicone Healthband. Those without an iPhone may be enrolled in the Device Share Program or the Android program when available. - The study team will deploy a light-weight silicone HealthBand with the team’s Corrie logo. It is a one-size fits all band with no native technology functionality at this time. Participants will be asked if they have a silicone allergy prior to offering the HealthBand. The band is optional. The purpose of the Healthband is to serve as an inpatient reminder to nurses and the treatment team that individual is part of study and as a “pledge” by the participant to improve health and engage with the app.

Date: 01/02/2020

Principal Investigator: [name], MD, MHS (Cardiology)

Application Number: IRB00099938

7. Study Statistics

- a. Primary outcome variable.
- b. Secondary outcome variables.
- c. Statistical plan including sample size justification and interim data analysis.
- d. Early stopping rules.

Study Statistics	
Primary outcome:	Time to first readmission within 30 days post discharge
Secondary outcome:	ED visits, observation visits, recurrent AMI, mortality, medication adherence, patient satisfaction scores, app usability, patient activation, user engagement, 12-month readmission, and cost-effectiveness

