Statistical plan including sample size justification and interim data analysis.	
Allowing for 10% of drop-outs during 30-day follow-up, the aim was to recruit N=200 in the intervention group and N=1,000 patients in the comparison group to provide around 90% power at the 2-sided 5% level of significance to detect a hazard ratio of 0.5 (ie, 50% reduction in a hazard of the intervention group), assuming 85% of patients in the comparison group survive or are not readmitted by the end of study (Stata stpower). The incident readmission rate of patients in our historical comparison group admitted to JHH and JHBMC was 16 cases per 100 person-months. We aim to detect a 50% risk reduction in readmission rates because our solution is comprehensive in nature and it is estimated that 76% of 30-day readmissions are potentially preventable using proven standards of care.
 
Our statistics will be primarily descriptive. We will examine characteristics of participants who join the study including demographics (e.g., age, sex, race/ethnicity, level of education, mHealth literacy, body mass index, marital status, occupation, annual income, insurance coverage) and clinical characteristics (e.g., severity of MI by TIMI/GRACE score, Killip Class, severity of cardiovascular disease by ejection fraction, medications, cardiac risk factor profile including dyslipidemia and lipid management characteristics as above), hypertension, diabetes, smoking, prior history of MI, and other comorbidities such as COPD, anxiety, and depression. We will examine primary and secondary outcomes as frequencies (percentage) for categorical variables and mean (SD) for continuous variables according to site of enrollment (JHH or JHBV) and type of mobile device (iPhone or Android). We will compare baseline characteristics of study participants using χ^2 and t-tests for categorical and continuous variables, as appropriate.
 
In assessing readmissions and cost-effectiveness, concurrent and historical controls will be matched to enrolled patients based on sociodemographic/clinical variables, and risk stratification using APR DRG / severity of illness scores (which are shown in the literature to be predictive for readmissions). We will conduct a Cox survival analysis to compare time to first readmission between the Corrie digital health group and the historical comparison group. We will build a Markov model of cost-effectiveness with the perspective of a hospital adopting Corrie technology, taking into account the lifelong outcome and cost of the Corrie discharge process versus the standard

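### The primary event does not separate scheduled from unplanned readmissions, and the collected reason for readmission is not used in the comparison

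*Combined protocol and SAP*

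**What the plan says.** Section 2 (Objectives) states the primary aim as "To assess time to first readmission within 30 days post-discharge from the hospital". The primary outcome row of Section 7 (Study Statistics) reads "Time to first readmission within 30 days post discharge". The Cox comparison in the statistical plan uses the same unqualified event. No section defines readmission as scheduled or unplanned, or says how a scheduled return followed by an unplanned one is handled.

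Section 4, under data collection for the primary outcome (item a), asks the hospitals' data managers for "readmission, days to readmission, reason for readmission, ED visits, observation visits, and mortality" in both groups. For the app group, cause of readmission is also checked in the records (Section 4, procedural steps). Neither source is tied to the event definition or to any analysis.

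The sample-size text in Section 7 aims for "around 90% power at the 2-sided 5% level of significance" "to detect a hazard ratio of 0.5", "assuming 85% of patients in the comparison group survive or are not readmitted by the end of study". The effect is set on readmission as a whole. The supporting argument is that "it is estimated that 76% of 30-day readmissions are potentially preventable using proven standards of care".

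The historical comparison group was admitted between 1 October 2015 and 1 October 2016, before the app was available (Section 4, Study duration).

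**The concern.** The app works through medication management, follow-up appointments and education. A return already booked at discharge, such as a staged procedure, is unlikely to respond to any of these. Taken literally, the endpoint counts such a return as an event and stops the patient's clock.

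Two consequences follow.

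- **Dilution.** If scheduled returns are equally frequent in both groups, they add events that carry no treatment effect. The HR moves toward 1 and power falls.
- **Confounding with calendar time.** The two groups come from different periods. If the practice of scheduling returns changed between them, the change enters the HR as though the app had caused it, or it masks a real effect. Matching on patient characteristics and severity scores, as Section 7 plans, does not remove a change in practice.

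There is also a question of timing. The reason field will be in hand but no rule governs it, so the choice between all and unplanned readmissions could be made after results are seen.

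**Working it through.** **Inputs from Section 7:** 200 app and 1,000 comparison patients; 85% of the comparison group event-free; HR 0.5; two-sided 5%; 10% drop-out.

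**Assumption:** a share f of the comparison-group readmission hazard is scheduled. The documents give no value, so f = 5%, 10% and 20% are used to show a range.

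**1. The plan's own figure.**
Expected events E = 200 × (1 − 0.85^0.5) + 1,000 × (1 − 0.85) = 15.6 + 150 = 165.6.
Schoenfeld power = Φ(√(E × 1/6 × 5/6) × |ln HR| − 1.96) = Φ(4.796 × 0.693 − 1.96) = Φ(1.364) = 91.4%.
After 10% loss (180 v 900), E = 149.0 and power is 88.4%. The stated figure of about 90% reproduces.

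**2. Dilution, with equal scheduled hazards in both periods and HR 0.5 on unplanned events only.**
HR for all readmissions = f + (1 − f) × 0.5. At f = 20% this is 0.20 + 0.80 × 0.5 = 0.60.
For unplanned events alone, the HR stays 0.5 and the comparison-group event-free proportion is 0.85^(1 − f).

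Schoenfeld power, 200 v 1,000 (180 v 900 in brackets):

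| f | HR, all | Power, all | Events, unplanned | Power, unplanned | Gain, points |
|---|---|---|---|---|---|
| 0% | 0.50 | 91.4% (88.4%) | 166 (149) | 91.4% (88.4%) | 0 |
| 5% | 0.525 | 87.2% (83.6%) | 158 (142) | 90.1% (86.9%) | 2.9 (3.3) |
| 10% | 0.55 | 82.1% (78.0%) | 150 (135) | 88.6% (85.2%) | 6.5 (7.2) |
| 20% | 0.60 | 69.6% (65.0%) | 135 (121) | 85.0% (81.1%) | 15.4 (16.1) |

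Log-rank simulation at 200 v 1,000 gives lower levels and the same pattern. Power is about 81-82% at f = 0. At f = 5%, 10% and 20% it is 76%, 70% and 58% on all events, against 79%, 76% and 71% on unplanned events. Repeat runs agree within about 1 to 2 points.

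The 9- to 10-point gap at f = 0 (91.4% against 81-82%) is a difference between formula and simulation. It has nothing to do with scheduled readmissions, so the simulated levels should not be set against the plan's 90%. The cost of the endpoint choice is the difference between the two analyses under one method. Over both methods and both sample sizes this is about 2-3, 6-8 and 13-16 points.

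**3. Change over time, with no app effect.**
Take f = 20% in 2015-16. If scheduled returns halve by the later period, HR = 0.80 + 0.20 × 0.5 = 0.90. If they double, HR = 0.80 + 0.20 × 2 = 1.20. Either error arises without any change in unplanned readmission.

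**4. Later unplanned readmissions hidden by a scheduled one.**
With independent constant hazards and f from 5% to 20%, a scheduled return precedes an unplanned one within 30 days in about 0.6 to 1.9 per 1,000 comparison patients, and in 0.06 to 0.2 of 200 app patients. This is negligible.

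**The case against.** Readmission for any reason is a legitimate endpoint. It needs no judgement about cause and comes from the same administrative source in both groups. Sorting by reason code adds misclassification, which could differ between the two periods. This stands, and it is why the unplanned analysis need not replace the all-readmission one.

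A reader might infer that the power calculation is broken. It is not. The plan sets HR 0.5 on all readmissions, and the stated power reproduces on that basis. What changes is the effect the app must have where it can act: HR = (0.5 − f)/(1 − f), which is 0.47 at f = 5% and 0.375 at f = 20%. That concerns how optimistic the target is.

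A reader might also take the 24% left over from the 76% preventable figure as the scheduled share. The documents do not say so, since an unplanned readmission can also be unpreventable.

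Nor do the documents say that scheduled returns are counted. They are silent, the hospitals' readmission field may already exclude planned stays, and the true share may be near zero.

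Finally, a general claim of bias toward 1 goes too far. It requires equal scheduled hazards in both periods, which nothing in the documents establishes.

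**Conclusion.** The point holds as a gap in the event definition and an unused data field. Scheduled readmissions can move the HR in either direction against a 2015-16 comparator, and they dilute it toward 1 if their rate did not change. The power gain from an unplanned analysis is small at a 5% scheduled share (2-3 points), moderate at 10% (6-8) and material only at 20% (13-16). All three shares are assumptions, and the gains further assume HR 0.5 on unplanned events and no app effect on scheduled ones. The documents do not support a claim that the sample size is wrong, that the bias has a known direction, or that hidden later readmissions matter. This is a cheap improvement, not a flaw that undermines the trial.

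**What to change.** - Before the app group's outcomes are linked, write a rule that classifies each readmission as scheduled or unplanned from the administrative reason field. Apply it identically to both groups, without knowledge of group. Admission dates reveal the group, so they should be withheld from whoever classifies.
- Prespecify a Cox analysis of time to first unplanned readmission within 30 days, in which a scheduled readmission is neither an event nor the end of follow-up. The data request should therefore cover every readmission in the 30 days, with its date and reason.
- Report this analysis beside the all-readmission analysis, with the number of scheduled readmissions in each group, so that any shift between periods is visible. The sponsor may make it the primary analysis. In that case the comparison-group rate and the power should be restated for that event.

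The cost is one classification rule and one more Cox model, using a field already requested. The downside is slightly fewer events (158 to 135 expected, against 166, for a 5% to 20% share) and some misclassification of reason codes, possibly different between the two periods.
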